5.5 Subject Withdrawal/Discontinuation Criteria

Subjects may withdraw consent at any time for any reason or be dropped from the trial at the discretion of the Investigator should any untoward effect occur. In addition, a subject may be withdrawn by the Investigator or the Sponsor if enrollment into the trial is inappropriate, the trial plan is violated, or for administrative and/or other safety reasons. Specific details regarding discontinuation or withdrawal are provided in Section 7.1.3 – Other Procedures.

A subject must be discontinued from the trial for any of the following reasons:

- AE as described above (section 5.3.2.3).
- The subject or legal representative (such as a parent or legal guardian) withdraws consent.
- Confirmed radiographic disease progression

Note: A subject may be granted an exception to continue on treatment with confirmed radiographic progression if clinically stable or clinically improved, please see Section 5.3.2.4

- Any clinical adverse event (AE), laboratory abnormality or intercurrent illness which, in the opinion of the investigator, indicates that continued participation in the study is not in the best interest of the subject
- Intercurrent illness that prevents further administration of treatment
- Investigator's decision to withdraw the subject
- The subject has a confirmed positive serum pregnancy test
- Noncompliance with trial treatment or procedure requirements
- The subject is lost to follow-up

- Administrative reasons

The End of Treatment visit procedures are listed in Section 6 (Protocol Flow Chart) and Section 7. After the end of treatment, each subject will be followed for 30 days for adverse event monitoring. Subjects who discontinue for reasons other than progressive disease will have post-treatment follow-up for disease status until disease progression, starting a non-study cancer treatment, withdrawing consent or becoming lost to follow-up. After documented disease progression, information on survival will be obtained until death, withdrawal of consent, or the end of the study, whichever occurs first.

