- a. General, assessments/procedures are to be performed on Day 1 and prior to the first dose of treatment for each cycle unless otherwise specified. Treatment cycles are 2 weeks; however the treatment cycle interval may be increased due to toxicity according to the dose modification guidelines.
- b. Written consent must be obtained prior to performing any protocol specified procedure. Results of a test performed prior to the subject signing consent as part of routine clinical management are acceptable in lieu of a screening test if performed within the specified time frame in the protocol. Subject number will be assigned when the study informed consent is signed.
- c. Prior medications – Record all medications taken within 30 days of screening visit. Concomitant medications – Enter new medications started during the trial through the Safety Follow-up visit. Record all medications taken for AEs.
- d. AEs and laboratory safety measurements will be graded per NCI CTCAE version 4.0. All AEs, whether gradable by CTCAE or not, will also be evaluated for seriousness.
- e. After informed consent has been obtained but prior to initiation of study drug, only serious adverse events caused by a protocol-mandated intervention should be reported. After initiation of study drug, all adverse events will be reported until 90 days after the last dose of study treatment or until initiation of another anti-cancer therapy, whichever occurs first. After this period, investigators should report any serious adverse events that are believed to be related to prior treatment with study drug. For subjects included and never treated with study drug, SAEs should be collected for 30 days from the date of inclusion. All SAEs must be followed to resolution or stabilization.
- f. Vital signs to include temperature, pulse, oxygen saturation, weight and blood pressure. Height will be measured at screening only. ECG is to be performed at screening, C5 day 1 and every 8th week thereafter, until disease progression or end of treatment with nivolumab.
- g. For women of childbearing potential, a serum pregnancy test should be performed within 24 hours prior to first dose of trial treatment. Pregnancy tests (serum and/or urine tests) should be repeated every 5 cycles (10 weeks) ± 7 days.

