8.1.3.4 Post-Treatment Visits

8.1.3.4.1 Safety Follow-Up Visit

The mandatory Safety Follow-Up Visit should be conducted approximately 30 days after the last dose of trial treatment or before the initiation of a new anti-cancer treatment, whichever comes first. All AEs that occur prior to the Safety Follow-Up Visit should be recorded. Subjects with an AE of Grade > 1 will be followed until the resolution of the AE to Grade 0-1 or stabilization, until the beginning of a new anti-neoplastic therapy, whichever occurs first. SAEs that occur within 90 days of the end of treatment or before initiation of a new anti-cancer treatment should also be followed and recorded.

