8.1.3.4.3 Survival Follow-up

Once a subject experiences confirmed disease progression or starts a new anti-cancer therapy, the subject moves into the survival follow-up phase. We will then monitor survival status by contacting the GP/local hospital or by phoning the patient every 3 month, until the end of the study. The survival status and, if applicable, the cause of death, will be recorded.

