9.2.1 Serious Adverse Event Collection and Reporting

The Investigator Brochure (IB) represents the Reference Safety Information to determine expectedness of serious adverse events for expedited reporting. Following the subject's written consent to participate in the study, all SAEs, whether related or not related to study drug, must be collected, including those thought to be associated with protocol-specified procedures. All SAEs must be collected that occur during the screening period and within 90 days of the last dose of nivolumab. If applicable, SAEs must be collected that relate to any later protocol-specified procedure (eg, a follow-up skin biopsy). For subjects included and never treated with study drug, SAEs should be collected for 30 days from the date of inclusion.

The investigator must report any SAE that occurs after these time periods and that is believed to be related to study drug or protocol-specified procedure.

An SAE report must be completed for any event where doubt exists regarding its seriousness.

If the investigator believes that an SAE is not related to study drug, but is potentially related to the conditions of the study (such as withdrawal of previous therapy or a complication of a study procedure), the relationship must be specified in the narrative section of the SAE Report Form.

SAEs, whether related or not related to study drug, and pregnancies, must be reported to Sponsor (or designee) within 24 hours of awareness of the event. SAEs must be recorded on the SAE Report Form; pregnancies on a Pregnancy Surveillance Form (electronic or paper forms).

If only limited information is initially available, follow-up reports are required.

If an ongoing SAE changes in its intensity or relationship to study drug or if new information becomes available, the SAE report must be updated and submitted within 24 hours to Sponsor (or designee) using the same procedure used for transmitting the initial SAE report.

All SAEs must be followed to resolution or stabilization.

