9.3 Nonserious Adverse Events

9.3.1 Nonserious Adverse Event Collection and Reporting

The collection of nonserious AE information should begin at initiation of study drug until 90 days from the last dose of study drug.

Nonserious AEs should be followed to resolution or stabilization, or reported as SAEs if they become serious. Follow-up is also required for nonserious AEs that cause interruption or discontinuation of study drug and for those present at the end of study treatment as appropriate. All identified nonserious AEs must be recorded and described on the nonserious AE page of the CRF.

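### New adverse events in days 31 to 90 after the last dose are actively reviewed in patients without progression but only passively captured in progressors

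*Combined protocol and SAP*

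**What the plan says.** **Length of the window.**
- Section 7.0, footnote e: "After initiation of study drug, all adverse events will be reported until 90 days after the last dose of study treatment", or until another anti-cancer therapy starts, whichever is first.
- Section 9.3.1: "The collection of nonserious AE information should begin at initiation of study drug until 90 days from the last dose of study drug".
- Section 9.2.1: "All SAEs must be collected that occur during the screening period and within 90 days of the last dose of nivolumab". Neither 9.2.1 nor 9.3.1 closes the window early when new therapy starts.
- Section 5.5, on the time after treatment ends: "each subject will be followed for 30 days for adverse event monitoring". Section 1.0 says the same but keeps 90 days for SAEs.
- Section 8.1.3.4.1: "The mandatory Safety Follow-Up Visit should be conducted approximately 30 days after the last dose of trial treatment", or before new anti-cancer treatment. AEs are recorded up to that visit; SAEs for 90 days or until new treatment.

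**Who is seen after day 30.** Sections 1.0, 5.5 and 8.1.3.4.2 give the follow-up visits to patients who have not progressed. For the others, Section 5.5 says: "After documented disease progression, information on survival will be obtained until death, withdrawal of consent, or the end of the study". Section 8.1.3.4.3 has the GP, local hospital or patient contacted every three months, and adds: "The survival status and, if applicable, the cause of death, will be recorded".

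**Flow chart.** After treatment, the adverse event review row is marked at the 30-day safety visit and in the Year 1 follow-up column. The Survival Follow-up column has no mark.

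**The concern.** The incidence, nature and severity of adverse events is the first primary outcome (Section 6.1). If the schedule is followed as drawn, whether anyone asks about a new event after day 30 depends on whether the tumour has progressed. Ascertainment of the primary outcome then follows a secondary outcome.

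Two results are exposed. Late event rates can come out too low. And exploratory objective 5, which looks for biomarkers of both response and toxicity, can show a toxicity-response association that arises only because responders were asked and progressors were not. In addition, after escalation the SMC is convened by counts of nivolumab-related Grade 3 or 4 events (Section 9.8), and an event that is never elicited cannot enter those counts.

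**Working it through.** The plan gives no figure to reproduce: N = 20 is stated in Section 11.1 without an event rate or precision target. The check is a comparison of passages, followed by limited arithmetic.

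**Step 1. The window, place by place**

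| Section | Non-serious AEs | SAEs | Closes at new therapy? |
|---|---|---|---|
| 1.0 | 30 days | 90 days | not stated |
| 5.5 | 30 days | not separated | not stated |
| 8.1.3.4.1 | to the visit at about day 30 | 90 days | yes |
| 7.0, footnote e | 90 days | 90 days | yes |
| 9.2.1 | – | 90 days | no |
| 9.3.1 | 90 days | – | no |

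SAEs are given 90 days wherever they are specified separately. For non-serious AEs the documents give both 30 and 90 days.

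**Step 2. Scheduled contacts after the last dose**

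| Time | Stopped without progression | Confirmed progression |
|---|---|---|
| about day 30 | safety visit with AE review | the same |
| about month 3 | visit with AE review, directed examination and laboratory tests | survival contact; survival status and cause of death |

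**Step 3. What differs.** The span after the safety visit is 90 − 30 = 60 days, or 60/90 = 67% of the window. Both groups go without a scheduled contact for most of it. The difference is the content of one contact at about month 3: one group is asked about adverse events and the other, on the text of 8.1.3.4.3, is not.

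**Step 4. When this falls.** Take progression at the Cycle 7 scan, with 14-day cycles and C1D1 = day 1. Cycle 6 is day 1 + 14 × 5 = 71 and Cycle 7 is day 1 + 14 × 6 = 85. Section 5.2 puts the end of radiotherapy two weeks before C5D1 (day 57), so at day 43.
- Last dose at Cycle 6: days 101 to 161, that is (101 − 43)/7 = 8.3 to (161 − 43)/7 = 16.9 weeks after radiotherapy.
- Last dose at Cycle 7: days 115 to 175, that is 10.3 to 18.9 weeks after radiotherapy.

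Section 2.1 itself describes serious late toxicity from re-irradiation.

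**Step 5. Size.** One patient is 1/20 = 5 percentage points, provided that patient has not already been counted for the same event earlier.

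For illustration only, let q be the true risk of a new AE in days 31 to 90, f the share of patients in survival follow-up with the window still open, and s the share of their events captured anyway. With full capture in the others, observed risk = q × [1 − f(1 − s)], and the relative under-count is f(1 − s). The documents give none of q, f or s. Assuming f = 0.4 to 0.8 and s = 0 to 0.5:
- smallest: 0.4 × 0.5 = 20%;
- largest: 0.8 × 1 = 80%.

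With q = 20%, 20 × 0.20 = 4.0 patients are expected, and between 4.0 × 0.8 = 3.2 and 4.0 × 0.2 = 0.8 would be seen. Patients who start new therapy early reduce f under footnote e, and the under-count shrinks with it. So wide a range shows direction, not size.

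**The case against.** - **The window is not 90 days for everyone.** Footnote e closes it when new anti-cancer therapy starts, and progressors are the patients most likely to start one. For them, the absence of later events is by design under that footnote. This stands. The gap is confined to progressors not on new therapy, and Sections 9.2.1 and 9.3.1 disagree with the footnote on this.
- **Under the 30-day text there is no gap for non-serious events.** This also stands as far as it goes. But 9.3.1 and footnote e say 90 days, and under either reading the Year 1 visits still collect later events from one group only.
- **SAEs are covered.** Section 9.2.1 requires SAEs to day 90 whatever the visit schedule, and 8.1.3.4.1 follows open events above Grade 1 in everyone until resolution, stabilisation or new therapy. This stands, but for progressors it depends on spontaneous report or on what the GP or hospital mentions; no enquiry is scheduled.
- **Progressors may attend.** Section 8.1.3.4.2 sends the remaining patients to follow-up without defining them, and footnote l limits some follow-up samples to patients not progressed, which suggests that others might come. Section 8.1.2.1 mentions telephone assessment of status just after a sentence on toxicity. The text is ambiguous, but Sections 1.0, 5.5 and 8.1.3.4.3 point the other way and the flow chart has no mark.

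**Conclusion.** The asymmetry is in the documents. New adverse events in days 31 to 90, chiefly non-serious ones, are actively sought once in patients without progression and only passively captured in progressors who have not started new therapy. The likely direction is a downward bias in AE incidence and a distorted toxicity-response comparison. The size cannot be derived: the progression share, the late event rate and the passive capture rate are all absent, and what can be said is 5 percentage points per missed patient.

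A reader might infer that late toxicity is largely missed in progressors, or that 67% of the window is lost in that group alone. The documents support neither. SAE collection and follow-up of open events continue for progressors, and the 67% span is not a difference between the groups.

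The conclusion assumes that progressors do not attend the Year 1 visits, which is the more natural reading but not an unambiguous one. It warrants an amendment because it touches the primary outcome and is cheap to correct; it does not invalidate the trial.

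**What to change.** 1. Reconcile Sections 1.0, 5.5, 7.0 (footnote e), 8.1.3.4.1, 9.2.1 and 9.3.1 into one stated collection window for non-serious AEs and one for SAEs, and say whether each closes at new anti-cancer therapy.
2. Define in 8.1.3.4.2 who the remaining patients are.
3. Make the first three-monthly survival contact, at about day 90 after the last dose, an AE/SAE review with the patient and not only the GP or hospital. It should cover events up to the end of the stated window and record the start date of any new anti-cancer therapy, so that later events can be separated.
4. Mark this review in the Survival Follow-up column of the flow chart and state it in 5.5 and 8.1.3.4.3.
5. In the analysis, tabulate days 0 to 30 and 31 to 90 separately and by reason for stopping, with the number of patients actually assessed as denominator. If the review in item 3 is not adopted, this table is the minimum needed to show the imbalance.

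The cost is protocol wording, one flow-chart mark, one CRF page and a slightly longer call. The contact itself is already planned.

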8.0 TRIAL PROCEDURES

8.1 Trial Procedures

The Trial Flow Chart - Section 6.0 summarizes the trial procedures to be performed at each visit. Individual trial procedures are described in detail below. It may be necessary to perform these procedures at unscheduled time points if deemed clinically necessary by the Investigator.

Furthermore, additional evaluations/testing may be deemed necessary by the Sponsor and/or Merck for reasons related to subject safety. In some cases, such evaluation/testing may be potentially sensitive in nature (e.g., HIV, Hepatitis C, etc.), and thus local regulations may require that additional informed consent be obtained from the subject. In these cases, such evaluations/testing will be performed in accordance with those regulations.

8.1.1 Administrative Procedures

8.1.1.1 Informed Consent

The Investigator must obtain documented consent from each potential subject prior to participating in a clinical trial.

8.1.1.1.1 General Informed Consent

Consent must be documented by the subject's dated signature or by the subject's legally acceptable representative's dated signature on a consent form along with the dated signature of the person conducting the consent discussion.

A copy of the signed and dated consent form should be given to the subject before participation in the trial.

The initial informed consent form, any subsequent revised written informed consent form and any written information provided to the subject must receive the IRB/ERC's approval/favorable opinion in advance of use. The subject or his/her legally acceptable representative should be informed in a timely manner if new information becomes available that may be relevant to the subject's willingness to continue participation in the trial. The communication of this information will be provided and documented via a revised consent form or addendum to the original consent form that captures the subject's dated signature or by the subject's legally acceptable representative's dated signature.

Specifics about a trial and the trial population will be added to the consent form template at the protocol level.

The informed consent will adhere to IRB/ERC requirements, applicable laws and regulations and Sponsor requirements.

8.1.1.2 Inclusion/Exclusion Criteria

All inclusion and exclusion criteria will be reviewed by the Investigator or qualified designee to ensure that the subject qualifies for the trial.

8.1.1.3 Medical History

A medical history will be obtained by the Investigator or qualified designee. Medical history will include all active conditions, and any condition diagnosed within the prior 10 years that are considered to be clinically significant by the Investigator. Details regarding the disease for which the subject has enrolled in this study will be recorded separately and not listed as medical history.

8.1.1.4 Prior and Concomitant Medications Review

8.1.1.4.1 Prior Medications

The Investigator or qualified designee will review prior medication use, including any protocol-specified washout requirement, and record prior medication taken by the subject within 28 days before starting the trial. Treatment for the disease for which the subject has enrolled in this study will be recorded separately and not listed as a prior medication.

8.1.1.4.2 Concomitant Medications

The Investigator or qualified designee will record medication, if any, taken by the subject during the trial.

8.1.1.5 Disease Details and Treatments

8.1.1.5.1 Disease Details

The Investigator or qualified designee will obtain prior and current details regarding disease status.

8.1.1.5.2 Prior Treatment Details

The Investigator or qualified designee will review all prior cancer treatments including systemic treatments, radiation and surgeries.

8.1.1.5.3 Subsequent Anti-Cancer Therapy Status

The Investigator or qualified designee will review all new anti-neoplastic therapy initiated after the last dose of trial treatment. If a subject initiates a new anti-cancer therapy within 30 days after the last dose of trial treatment, the 30 day Safety Follow-up visit must occur before the first dose of the new therapy. Once new anti-cancer therapy has been initiated the subject will move into survival follow-up.

8.1.1.6 Assignment of Subject Number

All consented subjects will be given a unique subject number that will be used to identify the subject for all procedures that occur during the screening period, and for all subjects eligible for treatment, during the treatment and follow-up period.

Each subject will be assigned only one subject number. Subject numbers must not be re-used for different subjects. Any subject who is screened multiple times will retain the original subject number assigned at the initial screening visit.

8.1.2 Clinical Procedures/Assessments

8.1.2.1 Safety Assessments

At baseline, a medical history will be obtained to capture relevant underlying conditions. The baseline examinations should include weight, height, ECOG Status, BP, HR, temperature and oxygen saturation by pulse oximetry at rest and should be performed within 28 days prior to first dose. Baseline signs and symptoms are those that are assessed within 14 days prior to first dose of study drug. Concomitant medications including steroid dose will be collected within 14 days prior to first dose of study drug through the study treatment period.

Baseline local laboratory assessments should be done within 14 days prior to first dose and are to include: CBC w/differential, LFTs (ALT, AST, total bilirubin, alkaline phosphatase), BUN or serum urea level, creatinine, albumin, Ca, Mg, Na, K, Cl, phosphate, LDH, glucose, amylase, lipase, TSH, free T4, and urine analysis.

The following baseline local laboratory assessments should be done within 28 days prior to first treatment: Hepatitis B and C testing (HBV sAg and HCV Ab or HCV RNA).

Pregnancy testing must be performed within 72 hours prior to Day 1 and then every 5 cycles (10 weeks) \pm 7 days.

While on-study the following local laboratory assessments are to be done within 3 days prior to each dose: CBC with differential, LFTs (ALT, AST, total bilirubin, alkaline phosphatase), BUN or serum urea level, creatinine, albumin (if clinically indicated), Ca, Mg, Na, K, Cl, phosphate, LDH, glucose, amylase, and lipase. Thyroid function testing is to be done every 6 weeks.

Subjects will be evaluated for safety if they have received any study drug. Toxicity assessments will be continuous during the treatment phase. During the safety follow-up phase toxicity assessments should be done in person. Once subjects reach the survival follow-up phase, either in person or documented telephone calls to assess the subject's status are acceptable.

Adverse events and laboratory values will be graded according to the NCI-CTCAE version 4.0.

The start and stop time of the study therapy infusions should be documented.

Additional measures, including non-study required laboratory tests, should be performed as clinically indicated or to comply with local regulations. Laboratory toxicities (eg, suspected drug induced liver enzyme evaluations) will be monitored during the follow-up phase via on site/local labs until all study drug related toxicities resolve, return to baseline, or are deemed irreversible.

Some of the assessments referred to in this section may not be captured as data in the CRF. They are intended to be used as safety monitoring by the treating physician. Additional testing or assessments may be performed as clinically necessary or where required by institutional or local regulations.

